#### 2.1.2 Primary endpoint (Part 1 and Part 2)

- **Proportion of patients with Clinical Remission at week 12**  
(defined as mMCS SFS=0 or 1, if drop  $\geq 1$  from BL; and RBS=0; and mESS $\leq 1$ )

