#### 2.1.3 Key Secondary endpoints (Part 2 / Phase III only)

- **Proportion of patients with Mucosal Healing at week 12**  
(defined as mESS  $\leq 1$ )
- **Proportion of patients with Clinical response at week 12**  
(defined as total MCS reduction  $\geq 3$  pts. and  $\geq 30\%$  from BL; AND RBS drop from baseline by  $\geq 1$ pt., or absolute RBS  $\leq 1$  pt)

*Note that for part 2 / Phase III only, the above-defined key secondary endpoints are included into the statistical testing strategy in a hierarchical manner subsequent to performance of the test on the primary endpoint. For further details, refer to [Section 7.2](#)*

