#### **2.1.5 Secondary endpoints (Part 1 / Phase II only)**

- **Proportion of patients with Mucosal Healing at week 12**
- **Proportion of patients with Clinical response at week 12**

[figure not shown]

Table 2.2.2:1 Definition of Clinical Outcomes

Type of Response	MCS subscore				Total MCS	Modified MCS
	RBS	mESS	SFS	PGA		
Clinical remission (CR)	0	≤1	0 or 1, and drop ≥1 from baseline			≤2
Total Clinical remission (tCR)	≤1	≤1	≤1	≤1	≤2	
Clinical response	≤1 or Reduction from BL ≥1	not missing	not missing	not missing	Reduction from BL ≥3 and ≥30%	
Symptomatic remission	0	≤1	0	≤1	≤2	

- Abbreviations: RBS – rectal bleeding score; mESS – modified endoscopic subscore; SFS – stool frequency score; PGA – physician’s global assessment;
- If greyed out, the corresponding criterion (in column) is not relevant to evaluate the corresponding type of response(in row)
- Total MCS is calculated as the sum of RBS, mESS, SFS and PGA
- Modified MCS is calculated as the sum of RBS, mESS and SFS
- Partial MCS is calculated as the sum of RBS, SFS and PGA

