### 3.3.2 Inclusion criteria

Each patient must meet all of the following inclusion criteria to be included into the trial:

1. 18 - 75 years, at date of signing informed consent, males or females
2. Diagnosis of ulcerative colitis  $\geq 3$  months prior to screening by clinical and endoscopic evidence corroborated by a histopathology report
3. Moderate to severe activity (total MCS 6 to 12 with a RBS  $\geq 1$  AND an SFS  $\geq 1$  AND mESS  $\geq 2$  within 7-28 days prior to first dose)
4. Endoscopic activity extending proximal to the rectum ( $\geq 15$  cm from anal verge)
5. Well-documented demonstration of inadequate response or loss of response or have had unacceptable side effects with approved doses of TNF $\alpha$  antagonists (infliximab, adalimumab, golimumab) and/or vedolizumab in the past as per definition in the CTP [Appendix 10.6](#) (screening of both TNF $\alpha$  antagonists-AND-Vedolizumab failure patients will be capped once 48 randomized patients in Part 1 and 117 randomized patients in Part 2 meet this criterion; patients who have already been screened at the time of the cap will continue to be randomized into the study)
6. May be receiving a therapeutic dose of the following:
  - Oral 5-ASA compounds, provided that dose has been stable for at least the 4 weeks immediately prior to randomisation, and/or
  - Oral corticosteroids ( $\leq 20$  mg per day of prednisone or equivalent), provided that dose has been stable for the 2 weeks immediately prior to randomisation, and/or
  - Oral budesonide ( $\leq 9$  mg per day) or beclomethasone dipropionate ( $\leq 5$  mg per day), provided that dose has been stable for the 2 weeks immediately prior to randomisation, and/or
  - Azathioprine, 6-MP or methotrexate, provided that dose has been stable for the 8 weeks immediately prior to randomisation.
  - Probiotics (e.g. *S. boulardii*) provided that dose has been stable for the 4 weeks immediately prior to randomisation.
7. Patients with extensive colitis or pancolitis of  $>10$  years duration or family history of colorectal cancer or personal history of increased colorectal cancer risk must have had a negative colorectal cancer screening within  $<1$  year prior to enrolment (otherwise to be done during screening colonoscopy).

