As noted with the sample size calculation for Part 1, the proportion of patients who achieve clinical remission on Placebo when a centrally-read endoscopy is used is typically very low [[R17-2467](#)]; therefore, for this trial, a fixed rate of 15% of patients achieving clinical remission on Placebo at week 12 will be considered for further sample size planning.

Based on an application of the defined testing strategy (see [Section 7.2](#)) regarding the different endpoints, a simulation based power calculation has been performed for sample size assessment on both the primary and key secondary endpoints. For this purpose a correlation of 0.5 has been assumed between the different endpoints.

[Table 7.7.2: 2](#) presents scenarios for the planning of this trial whereby a difference versus Placebo of 0.20 is assumed for the proportion of patients who achieve clinical remission at week 12 (the primary endpoint). Calculations were performed using a 1-sided overall alpha level of 0.025 with a truncated Hochberg correction (‘truncation fraction’ = 1/2) applied to correct for multiplicity as a result of performing 2 treatment comparisons versus Placebo.

In line with the expected treatment benefit on the primary endpoint of clinical remission, it is also required that the magnitude of the BI655130 (SPESOLIMAB) response on key secondary endpoints, i.e., both the proportion of patients with mucosal healing and the proportion of patients with clinical response be at least 0.20 larger than the corresponding effect on placebo. Assuming therefore, an overall type 1 error= 0.025 (1-sided), a difference of 0.20 for each BI655130 (SPESOLIMAB) dose relative to Placebo in mucosal healing (rate assumed for each dose of BI655130 (SPESOLIMAB): 0.35, and placebo: 0.15), and a difference of 0.25 in clinical response (rate assumed for each dose of BI655130 (SPESOLIMAB): 0.60, and placebo: 0.35), and given the total of 390 patients (130 per treatment arm), the overall power that both/at least one dose(s) of BI655130 (SPESOLIMAB) would achieve statistical significance versus placebo for the primary and both key secondary endpoints will be approximately 81%/96% respectively (with a graphical approach used to attribute the remaining  $\alpha'$  from the test on the primary endpoint in order to correct for multiplicity because of multiple endpoints as well as two doses of BI655130 (SPESOLIMAB)). Note that alpha passing, for the case when both doses of BI655130

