(SPESOLIMAB) are statistically significant on the primary endpoint and one dose is subsequently statistically significant on all endpoints in the secondary family (key secondary and secondary), is not considered in the sample size evaluation.

Table 7.7.2: 1 Power to achieve statistical significance for the primary endpoint (clinical remission) and both key secondary endpoints (mucosal healing and clinical response) on both doses of BI655130 (SPESOLIMAB) under various scenarios

Scenario	Population Response Rate			Overall power to achieve all 3 endpoints	
	Clinical remission (H/L/P)	Mucosal Healing (H/L/P)	Clinical Response (H/L/P)	Power for both doses of BI655130 (SPESOLIMAB) to be stat. sig.	Power for at least one dose of BI655130 (SPESOLIMAB) to be stat. sig.
+	0.35/0.35/0.15	0.35/0.35/0.15	0.60/0.60/0.35	81.4%	95.6%
Sub-optimal	0.30/0.30/0.15	0.30/0.30/0.15	0.60/0.60/0.35	49.1%	77.2%
Minimal	0.25/0.25/0.15	0.25/0.25/0.15	0.60/0.60/0.35	13.5%	36.0%
++	0.40/0.40/0.15	0.40/0.40/0.15	0.60/0.60/0.35	92.3%	98.9%
↓ Placebo +	0.30/0.30/0.10	0.30/0.30/0.10	0.60/0.60/0.35	88.2%	97.9%
↓ low dose BI	0.35/0.30/0.15	0.35/0.30/0.15	0.60/0.55/0.35	57.8%	89.8%

Table 7.7.2:2 Power to achieve statistical significance for the primary endpoint (clinical remission) on both doses of BI655130 (SPESOLIMAB) under various scenarios

Scenario	Population Response Rate			Expected Response Difference	N per treatment group (1:1:1)	Power for both doses of BI655130 (SPESOLIMAB) to be stat. sig.	Power for at least one dose of BI655130 (SPESOLIMAB) to be stat. sig.
	High dose BI	Low dose BI	Placebo				
+	0.35	0.35	0.15	0.20	130	92.5%	98.6%
Sub-optimal	0.30	0.30	0.15	0.15	130	69.2%	88.9%
Minimal	0.25	0.25	0.15	0.10	130	31.3%	58.1%
++	0.40	0.40	0.15	0.25	130	99.0%	99.9%
↓ Placebo +	0.30	0.30	0.10	0.20	130	96.6%	99.6%
↓ low dose BI	0.35	0.30	0.15	0.20/0.15	130	78.7%	96.5%

To be noted that the sample size for Part 2 of the study may be adapted based on results from Part 1 in which case a protocol amendment will be required.

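### Part 2 power of 81%/96% assumes a 0.5 correlation between remission and mucosal healing that their definitions and equal rates rule out; at the table's own rates it is about 86%/97%

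*Protocol*

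**What the plan says.** Protocol 7.7.2 reports a simulation of power for the primary and key secondary endpoints and states: "For this purpose a correlation of 0.5 has been assumed between the different endpoints". It does not say whether 0.5 applies to the patients' binary outcomes, to a latent scale or to the test statistics.

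For mucosal healing the text has "rate assumed for each dose of BI655130 (SPESOLIMAB): 0.35, and placebo: 0.15", the same rates as for clinical remission. With 130 per arm, the power for both doses and for at least one dose is given as "approximately 81%/96% respectively". Table 7.7.2:1 ("Power to achieve statistical significance for the primary endpoint (clinical remission) and both key secondary endpoints (mucosal healing and clinical response) on both doses") has six scenarios. In each one the remission and healing rates are identical for high dose, low dose and placebo.

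The definitions stand elsewhere:
- **Clinical remission** (Protocol 2.1.2 and 7.1) is a conjunction: the stool-frequency condition, then "from BL; and RBS=0; and mESS" of 1 or less.
- **Mucosal healing** (Protocol 2.1.3, "Proportion of patients with Mucosal Healing at week 12", and 5.1) is mESS of 1 or less and nothing more.
- **Clinical response** (Table 2.2.2:1) asks of the total score "Reduction from BL ≥3 and ≥30" percent, plus a rectal bleeding condition.
- **Entry** (Protocol 3.3.2, criterion 3) requires "Moderate to severe activity (total MCS 6 to 12 with a RBS" of at least 1, SFS of at least 1 and mESS of at least 2.

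**The concern.** A patient cannot be in clinical remission without meeting the healing criterion, because both use the same endoscopic score. Non-response imputation does not break this: a remission success needs an observed mESS of 1 or less, and rescue turns both endpoints into failures. If one event lies inside another and the two have equal probability, they coincide in every patient. The equal rates in Table 7.7.2:1 and the 0.5 in the text therefore cannot both describe this trial.

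At stake is the power for winning all three endpoints. If remission and healing are one event, the healing test is nearly free once remission has been won, and the joint power is higher than stated. If healing is really more common than remission, the equal rates are wrong, and the joint power could be higher or lower. Protocol 7.7.2 allows the Part 2 sample size to be adapted after Part 1, so a decision made from this table would start from figures that do not fit the endpoints.

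**Working it through.** **Inputs.** From Protocol 7.7.2: 130 per arm and the rates in Table 7.7.2:1. From Protocol 7.2: one-sided alpha 0.025 and truncated Hochberg, so both doses win if both p-values are at most 0.01875, otherwise the smaller p-value must be at most 0.0125. Healing, then response, are tested at 0.0125 per dose if both doses won, or at 0.00625 for a single winning dose. As in 7.7.2, alpha is not passed between doses. The test is a pooled z-test without continuity correction.

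**Step 1: check the set-up on the primary endpoint.** The simulation reproduces all 12 figures of Table 7.7.2:2 within 0.1 point (for example 92.5/98.6 in the base row and 31.2/58.1 in the minimal row, against a stated 31.3/58.1).

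**Step 2: reproduce the stated figures.** All pairs of endpoints have correlation 0.5 on the binary scale (200,000 runs; both doses / at least one dose):

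| Row | Stated | Reproduced |
|---|---|---|
| Base (+) | 81.4/95.6 | 81.5/95.8 |
| Sub-optimal | 49.1/77.2 | 49.3/77.5 |
| ++ | 92.3/98.9 | 92.4/99.0 |
| Lower low dose | 57.8/89.8 | 58.0/90.3 |

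So the table was computed with 0.5, remission and healing included. The other two rows cannot be run this way. For rates p < q the largest binary correlation is √[p(1−q)/((1−p)q)]. For remission 0.25 with response 0.60 this is √(0.25×0.40/(0.75×0.60)) = 0.471. For 0.10 with 0.35 it is √(0.10×0.65/(0.90×0.35)) = 0.454. Both are below 0.5.

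**Step 3: apply the same formula to remission and healing.** With p = q it gives 1, and because remission is nested in healing the maximum is attained. To keep 0.5 under nesting, healing h would have to satisfy (1−h)/h = 0.25×(1−p)/p. For p = 0.35 that is 0.464, so h = 0.68. For p = 0.15 it is 1.417, so h = 0.41. The table has 0.35 and 0.15.

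**Step 4: how far the definitions fix the link with response.** I enumerated baseline scores allowed by criterion 3 (RBS 1–3, SFS 1–3, mESS 2–3, PGA 0–3, total 6–12) against week-12 scores that meet remission, with any PGA. Of 912 combinations, 883 meet clinical response. In each of the other 29, PGA is worse than at baseline. These are combinations, not patients, but they show that a remitter is a responder unless PGA worsens or is missing.

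**Step 5: recompute with remission and healing as one event** (400,000 runs, Monte Carlo standard error below 0.1 point). Column A keeps binary correlation 0.5 with response where feasible. Column B places remission inside response and assumes no correlation value.

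| Row | Stated | A | B |
|---|---|---|---|
| Base (+) | 81.4/95.6 | 85.5/96.6 | 86.1/96.8 |
| Sub-optimal | 49.1/77.2 | 61.0/83.0 | 61.2/83.1 |
| Minimal | 13.5/36.0 | infeasible | 24.6/48.4 |
| ++ | 92.3/98.9 | 92.9/99.0 | 93.0/99.0 |
| Lower placebo | 88.2/97.9 | infeasible | 90.0/98.3 |
| Lower low dose | 57.8/89.8 | 65.6/92.1 | 66.7/92.3 |

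Repeat runs of column B agree within 0.3 point. Across pooled, unpooled and normal-approximation tests, and a response correlation from 0 to full nesting, the base row stays within 84.1–87.1% for both doses and 96.1–97.1% for at least one.

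**Step 6: healing more common than remission (assumption only; the documents give no such rates).** Remission is 0.35 vs 0.15 and response 0.60 vs 0.35, with remission inside both other endpoints. The first figure takes healing and response as independent among non-remitters, the second as overlapping as far as possible:
- healing 0.40 vs 0.20: 80.0/95.1 and 80.9/95.4
- healing 0.45 vs 0.25: 75.7/93.7 and 77.2/94.1

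**The case against.** The strongest reply is that nesting, equal rates and 0.5 conflict, but the documents do not say which planning input is wrong. Equal rates may be the simplification, since 7.7.2 frames the key secondary differences as a minimum requirement of 0.20. With healing above remission, the assumed cases in Step 6 give both-dose power equal to or below the stated 81%. This stands: 86%/97% is the value at the table's own rates, and the direction of error is not settled beyond them.

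A second reply concerns scale. If 0.5 is applied to normally approximated arm proportions, all six rows reproduce within 0.8 point, including minimal (13.7/35.8) and lower placebo (88.5/98.4). On the scale of treatment differences, the largest possible correlation with response in the minimal row is (0.25×0.40 + 0.15×0.65)/√[(0.1875+0.1275)(0.24+0.2275)] = 0.51, so 0.5 is attainable there. In the lower-placebo row it is 0.49. The infeasibility in Step 2 therefore belongs to the binary reading only. This does not rescue 0.5 between remission and healing: identical events have correlation 1 on every scale.

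Third, little depends on it. Protocol 7.2 designs Part 2 to show at least one dose superior on remission. Neither that power nor type I error control uses this correlation. In the base row the at-least-one-dose figure moves by about 1 point, and the large gaps sit in pessimistic scenarios. SAP section 3 says seamless conduct of Part 2 is no longer viable after early termination. This also stands, and it limits the weight of the point rather than its correctness.

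**Conclusion.** The inconsistency is real, and nothing elsewhere in the documents resolves it. The 81%/96% rests on an input that the endpoint definitions exclude at the rates used.

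At those rates the stated figures are conservative (both doses / at least one dose):
- base row: 4 to 5 points / about 1 point
- sub-optimal row: about 12 / 6 points
- minimal row: about 11 / 12 points
- lower-low-dose row: 8 to 9 / 2 to 3 points
- ++ and lower-placebo rows: 2 points or less

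This assumes pooled z-tests and the alpha rules of Protocol 7.2 without alpha passing. The treatment of response matters little. Away from equal rates, the direction depends on healing rates the documents do not supply.

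Severity is minor. The primary claim, the testing procedure and type I error control are unaffected, and the point gives no reason to think 130 per arm too few at the table's rates.

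**What to change.** Rerun Table 7.7.2:1 with mucosal healing simulated as a superset of clinical remission, at healing rates equal to or above the remission rates over a justified range. State the scale of the correlation with clinical response, and choose a value that is feasible in every row and consistent with the response definition. Then restate the table and the 81%/96% in the text of 7.7.2, whatever the rerun shows.

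The cost is one simulation rerun and the corrected table and paragraph. No change to the testing procedure or to 130 per arm is requested. The rerun will show whether the three-endpoint power is as intended.

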## **8. INFORMED CONSENT, TRIAL RECORDS, DATA PROTECTION, PUBLICATION POLICY, AND ADMINISTRATIVE STRUCTURE**

The trial will be carried out in compliance with the protocol, the ethical principles laid down in the Declaration of Helsinki, in accordance with the ICH Harmonized Tripartite Guideline for Good Clinical Practice (GCP), relevant BI Standard Operating Procedures (SOPs), the EU regulation 536/2014 the Japanese GCP regulations (Ministry of Health and Welfare Ordinance No. 28, March 27, 1997) and other relevant regulations.

Standard medical care (prophylactic, diagnostic and therapeutic procedures) remains the responsibility of the treating physician of the patient.

The investigator will inform the sponsor immediately of any urgent safety measures taken to protect the trial patients against any immediate hazard, as well as of any serious breaches of the protocol or of ICH GCP.

The Boehringer Ingelheim transparency and publication policy can be found on the following webpage: [trials.boehringer-ingelheim.com](http://trials.boehringer-ingelheim.com). The rights of the investigator and of the sponsor with regard to publication of the results of this trial are described in the investigator contract. As a rule, no trial results should be published prior to finalization of the Clinical Trial Report. The certificate of insurance cover is made available to the investigator and the patients, and is stored in the ISF.

### **8.1 TRIAL APPROVAL, PATIENT INFORMATION, INFORMED CONSENT**

This trial will be initiated only after all required legal documentation has been reviewed and approved by the respective Institutional Review Board (IRB) / Independent Ethics Committee (IEC) and competent authority (CA) according to national and international regulations. The same applies for the implementation of changes introduced by amendments.

Prior to patient participation in the trial, written informed consent must be obtained from each patient (or the patient's legally accepted representative) according to ICH / GCP and to the regulatory and legal requirements of the participating country. Each signature must be personally dated by each signatory and the informed consent and any additional patient-information form retained by the investigator as part of the trial records. A signed copy of the informed consent and any additional patient information must be given to each patient or the patient's legally accepted representative."

The investigator or a designee must give a full explanation to trial patients based on the patient information form. A language understandable to the patient should be chosen, technical terms and expressions avoided, if possible.

The patient must be given sufficient time to consider participation in the trial. The investigator or a designee obtains written consent of the patient's own free will with the informed consent form after confirming that the patient understands the contents. The investigator or a designee must sign (or place a seal on) and date the informed consent form.

If a trial collaborator has given a supplementary explanation, the trial collaborator also signs (or places a seal on) and dates the informed consent.

Re-consenting may become necessary when new relevant information becomes available and should be conducted according to the sponsor's instructions.

The consent and re-consenting process should be properly documented in the source documentation.

## 8.2 DATA QUALITY ASSURANCE

A quality assurance audit/inspection of this trial may be conducted by the sponsor, sponsor's designees, or by IRB / IEC or by regulatory authorities. The quality assurance auditor will have access to all medical records, the investigator's trial-related files and correspondence, and the informed consent documentation of this clinical trial.

## 8.3 RECORDS

CRFs for individual patients will be provided by the sponsor. See [Section 4.1.5.2](#) for rules about emergency code breaks. For drug accountability, refer to [Section 4.1.8](#).

### 8.3.1 Source documents

In accordance with regulatory requirements the investigator should prepare and maintain adequate and accurate source documents and trial records that include all observations and other data pertinent to the investigation on each trial patient. Source data as well as reported data should follow good documentation practices and be attributable, legible, contemporaneous, original and accurate. Changes to the data should be traceable (audit trail). Data reported on the CRF must be consistent with the source data or the discrepancies must be explained.

The current medical history of the patient may not be sufficient to confirm eligibility for the trial and the investigator may need to request previous medical histories and evidence of any diagnostic tests. In this case the investigator must make three documented attempts to retrieve previous medical records. If this fails a verbal history from the patient, documented in their medical records, would be acceptable.

During the site visit the sponsor's CRA or auditor must be granted access to the original patient file (please see [Section 8.3.2](#)). The investigator must ensure that all patient identifiers (e.g. patient's name, initials, address, phone number, social security number) have properly been removed or redacted from any copy of the patients' source documents before sending them to the sponsor.

If the patient is not compliant with the protocol, any corrective action e.g. re-training must be documented in the patient file.

For the CRF, data must be derived from source documents, for example:

- Patient identification: gender, year of birth (in accordance with local laws and regulations)

- Patient participation in the trial (substance, trial number, patient number, date patient was informed)
- Dates of patient's visits, including dispensing of trial medication
- Medical history (including trial indication and concomitant diseases, if applicable)
- Medication history
- Adverse events and outcome events (onset date (mandatory), and end date (if available))
- Serious adverse events (onset date (mandatory), and end date (if available))
- Concomitant therapy (start date, changes)
- Originals or copies of laboratory results and other imaging or testing results, with proper documented medical evaluation (in validated electronic format, if available)
- Completion of patient's participation in the trial" (end date; in case of premature discontinuation document the reason for it).
- Prior to allocation of a patient to a treatment into a clinical trial, there must be documented evidence in the source data (e.g. medical records) that the trial participant meets all inclusion criteria and does not meet any exclusion criteria. The absence of records (either medical records, verbal documented feedback of the patient or testing conducted specific for a protocol) to support inclusion/exclusion criteria does not make the patient eligible for the clinical trial.

